In a case report by Baker and Wilson²³ examining Astym in the treatment of a bilateral carpal tunnel syndrome (CTS) patient, they found that Astym was shown to be an effective treatment approach for resolving the patient's symptoms. An article by Ettema et al²⁷ reported on the physiological changes that occur in the subsynovial layer of tissue during carpal tunnel. An electron microscope found fibrotic changes as a result of a shearing injury. The anatomy of the flexor tendons are similar to that of the tendons involved in de Quervain's. If Astym has been shown to be an effective treatment approach for

CTS, then it is reasonable to hypothesize that Astym would be an effective treatment for de Quervain's tenosynovitis. But does the Astym treatment along with stretching and exercise work better than the gold standard of care of splinting and exercise alone.

- **Study design:**

The research question for this study is:

Does adding an Astym treatment protocol to existing standard of care treatment of de Quervain's tenosynovitis increase outcomes of individuals with this condition?

The Alternative Hypothesis for this study is:

Participants receiving the Astym treatment protocol will have greater improvements in pain reduction and function as compared to those subjects in the control group receiving the standard of care therapy treatment

This is a randomized controlled study using repeated measure design with 2 groups:

- A. Control group who will receive standard of care rehabilitation intervention for the treatment of de Quervain's tenosynovitis.
- B. Experimental group will receive standard of care rehabilitation interventions plus Astym treatment protocol.

Three outcomes measures will be used for the study:

1. **Numeric Rating Scale for Pain**- This scale is a single point scale from 0-10. The participant picks one number to represent their pain, where 0 represents no pain and 10 represents worst pain imaginable.
2. **Quick Dash**-This is an 11 item questionnaire in which participants self-score themselves using a 1-5 point scale. One represents no difficulty in performing task whereas 5 represents unable to perform task.
3. **Sequential Occupational Dexterity Assessment**-This is a test to measure dexterity and bimanual abilities in activities of daily living. It includes 12 tasks with participants being scored on their ability, difficulty and pain during the task.

II. Characteristics of research population

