- Thumb abduction and extension with yellow power web or light resistance rubber bands 3 sets of 10 reps
- Continue stretching 4x/day for 30-45 seconds, with stretching prior to and after exercises:
 - UD of wrist with thumb tucked under fingers and wrist in neutral
 - Wrist flexion with elbow extended forearm pronated
 - Wrist extension with elbow extended forearm supinated

Phase III: Continue therapy, incorporate strengthening and functional movements for forearm, elbow and shoulder and prepare patient for discharge to home exercise program

- Goals include: Pain free functional use of affected extremity during all tasks without use of splint
- Replace moist heat pack with Upper Body Ergometer for 10 min
- **Continue Astym to affected extremity per de Quervain's protocol, including de Quervain's strokes for a max of 12 sessions**
- Continue stretching 4x/day for 30-45 seconds, with stretching prior to and after exercises:
 - UD of wrist with thumb tucked under fingers and wrist in neutral
 - Wrist flexion with elbow extended forearm pronated
 - Wrist extension with elbow extended forearm supinated
- Adding multi joint strengthening exercises to match job demands using dumbbells
- Patient discharged to HEP after 12 sessions of therapy with review of ergonomics, stretches, and exercises at last session.

Three months after discharge from CMC, Quick DASH and VAS scale scores and questionnaire regarding patient compliance will be completed by phone interview.

Data Analysis and Monitoring

Descriptive statistics will be used along with inferential statistics. The alternative hypothesis will be addressed using a mixed design analysis of variance to test for differences between-groups and within-groups. In addition we will also analyze the interaction effect between study group and time. All analyses will have an alpha of 0.05. Malchy's test for sphericity will be performed along with a Bonferroni comparison. If Malchy's test for sphericity is significant then a Greenhouse-Geisser or Huynh-Feldt correction will be used. In addition a repeated measure MANOVA may be used to test the dependent variables in a multivariate method if in fact the dependent variables demonstrate a relationship of linearity.

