Based upon the planned analyses for the primary hypothesis, a mixed repeated measure design with 1 between factor (group membership) and 1 within factor (repeated measures) has 2 groups with 16 subjects each for a total of 32 subjects. This design achieves a 80% power to test the between factor using the above mentioned mixed methods ANOVA using a 5% significance level with an actual Cohen's F effect size of .398

Data Storage and Confidentiality

All written data will be stored in a locked draw of a locked office. For data analysis purposes all data will also be stored using Microsoft Excel/ReCap Software. To ensure confidentiality all participants will be categorized alphanumerically.

IV. Risk/Benefit Assessment

- Risk

Potential side effects of Astym treatment include:

- 1) Ecchymosis to the treatment area, typically where fibrotic tissue and healing is indicated.
- 2) Increased pain or soreness for 24-48 hrs after treatment.
- 3) Increased inflammation of affected extremity after treatment.
- 4) Vagal response during treatment due to neural effect on tissue from the Astym treatment that include but are not limited to light headedness, feeling faint and nausea.

- Protection against risks

Patient education of these risks will help the patient understand some of the temporary side effects that they may experience. Icing 3-4 hrs after treatment can limit some of the side effects and help with pain and inflammation. Eating 1 hour prior to treatment will also limit vagal response during the Astym treatment. Prior to therapy, the patients will be encouraged to tell their therapist to stop treatment if they do not wish to continue if they are experiencing any of these symptoms and/or do not wish to continue in the study.

- Potential benefits to subjects:

Patients will receive Astym treatment to the affected extremity in addition to traditional therapy they would normally receive when being treated for de Quervain's tenosynovitis. Astym treatment will be delivered by a qualified, specially trained occupational therapist where instruments will be applied topically to the skin with moderate pressure to stimulate a healing and regenerative response. . We believe the additional Astym protocol will increase functional levels for patients along with a greater social benefit of the knowledge gained from this experimental study.

- Subject Compensation:

There will be no compensation to patients for this study.

V. Investigators Qualifications & Experience

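### No primary outcome, time point or success rule is named, and the powered between-group test is not a direct test of the improvement hypothesis

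*Combined protocol and SAP*

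**What the plan says.** Section I, Study design, states that "Three outcomes measures will be used for the study" (a pain scale, QuickDASH and SODA) and ranks none of them. The alternative hypothesis is that Astym patients "will have greater improvements in pain reduction and function" compared with controls.

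Section III, Methods and procedures, item iii, places measurements at baseline and at discharge after 12 sessions. QuickDASH and pain are asked again by phone at 3 months. SODA therefore has two occasions and the other two outcomes have three.

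Section III, Data Analysis and Monitoring, plans a mixed-design ANOVA with between-group and within-group tests, and continues: "In addition we will also analyze the interaction effect between study group and time". It sets the level with "All analyses will have an alpha of 0.05". It then says that Mauchly's "test for sphericity will be performed along with a Bonferroni comparison". Finally: "In addition a repeated measure MANOVA may be used to test the dependent variables in a multivariate method", on condition that the outcomes are linearly related.

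The power paragraph opens with "Based upon the planned analyses for the primary hypothesis" and says "This design achieves a 80% power to test the between factor", with 16 per group, a 5% level and Cohen's f of .398.

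**The concern.** A primary hypothesis is mentioned, but no outcome, time point or combination of results is tied to it. If pain is significant and function is not, or the group effect is significant and the interaction is not, the plan gives no agreed reading. The rule could then be chosen after the results are known, and the chance of a false claim for Astym would depend on that choice.

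The hypothesis is also about change, while the stated power belongs to the group main effect. With baseline among the repeated measures, that effect averages over an occasion where randomisation makes the expected difference zero. The group-by-time test does address improvement, but it is listed as an addition and no power is given for it.

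Two outcome definitions are open as well. Pain is a Numeric Rating Scale in Study design, but a VAS in Methods and procedures item iii, in Research design and in the 3-month paragraph. SODA is scored on ability, difficulty and pain, and no score is chosen for analysis.

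**Working it through.** **Inputs from the plan.** 16 per arm (N = 32), f = 0.398, 5% level, three outcomes, with occasions as listed above. **Assumed, because the plan gives neither:** within-patient correlation ρ (0.3, 0.5, 0.7) and between-outcome correlation (0 to 0.9). Equal variances and no dropout are also assumed.

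**Step 1: the plan's 80%.** For the between factor with m occasions, λ = f²·N·m / (1 + (m−1)ρ), referred to F(1,30).
- m = 3, ρ = 0.4: 0.398² × 32 × 3 / 1.8 = 8.45, power 80.3%.
- m = 2, ρ = 0.2: 0.398² × 32 × 2 / 1.2 = 8.45, power 80.3%.

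The 80% is attainable. It cannot be confirmed, because m and ρ are not stated. In this formula f is the difference averaged over all occasions.

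**Step 2: power for improvement.** With two groups, d = 2f = 0.796. Two meanings are possible.

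*Reading A: 0.796 SD at each follow-up, none at baseline.* The averaged difference is d(m−1)/m, so λ = 8·[d(m−1)/m]² / [(1+(m−1)ρ)/m]. At m = 3, ρ = 0.5: 8 × 0.531² / 0.667 = 3.38, power 42.8%. For the baseline-adjusted discharge comparison, λ = 8d²/(1−ρ²) on F(1,29). At ρ = 0.5: 8 × 0.634 / 0.75 = 6.76, power 71.0%.

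*Reading B: 0.796 SD is the average over three occasions.* With none at baseline, each follow-up difference is 0.796 × 3/2 = 1.19 SD.

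| Power, ρ = 0.3 / 0.5 / 0.7 | Reading A | Reading B |
|---|---|---|
| Between factor, 3 occasions | 51 / 43 / 37% | 85 / 76 / 68% |
| Between factor, 2 occasions (SODA) | 27 / 24 / 22% | not computed |
| Baseline-adjusted discharge (formula) | 63 / 71 / 86% | 93 / 96 / 99% |

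Simulation of the adjusted comparison under reading A gives 61/69/85%.

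**Step 3: false positives favouring Astym.** Each two-sided 0.05 test gives 2.5% in that direction. With independent tests:
- any of six (three outcomes × group or group-by-time): 1 − 0.975⁶ = 14.1%
- any of three: 1 − 0.975³ = 7.3%
- pain plus QuickDASH or SODA, by either test: (1 − 0.975²) × (1 − 0.975⁴) = 0.049 × 0.096 = 0.5%
- any of six at 0.05/3: 1 − (1 − 0.05/6)⁶ = 4.9%

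For correlated outcomes these were simulated under no effect (16 per arm; for the rules at 0.05, ρ = 0.5 and 20,000 trials per setting). A significant three-occasion interaction counted as favouring Astym if the average post-baseline change did.

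| Rule | Favouring Astym, between-outcome correlation 0 to 0.9 |
|---|---|
| Any of six tests | about 9-14% (17-26% in either direction) |
| Any of three between-factor tests | about 4-7% |
| Any of three group-by-time tests | about 5-7% (down to about 4% in a second simulation) |
| Pain plus a function measure | about 0.5-4% |
| Any of six, Bonferroni 0.05/3 across outcomes | about 3-5% |
| One pre-named test | 2.5% |

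In the 20,000-trial runs, changing ρ to 0.3 or 0.8 moves the figures for the rules at 0.05 by at most about one point. A fixed order of pain, QuickDASH, SODA on the adjusted discharge comparison gives 2.4-2.6%.

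**The case against.** The best case for the plan has four parts.

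- **Bonferroni is mentioned.** If it was meant across the three outcomes, the any-of-six figure falls to 3-5%. Beside the sphericity test it reads more like post-hoc comparisons of time points, but the text does not say. Control is therefore unknown. A reader might infer that there is definitely none; the documents do not support that.
- **The six-test rule is the loosest reading.** The interaction is introduced as an addition, separate ANOVAs per outcome are implied rather than stated, and the 14% end needs uncorrelated outcomes although SODA itself scores pain. The hypothesis wording suggests pain and function together, for which the figure is 0.5-4%. This stands as a limit on the size, but nothing in the plan requires both.
- **The hypothesis is not left untested.** Group-by-time is planned. The mismatch is in what the power statement covers, not in a missing analysis.
- **The stated power can be right.** Under reading B, 80% is reached at ρ of about 0.4. A reader might infer that the true power is 37-51%, but that holds only under reading A. Reading B needs a follow-up difference of 1.19 SD, which may be optimistic, but that is a different criticism.

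It is also fair that naming one outcome, one time point and one planned test would by itself settle the error rate. The baseline adjustment is recommended for precision. Over baseline and discharge, the group-by-time test has variance proportional to 2(1−ρ), against 1−ρ² for the adjusted comparison. The ratio of adjusted to unadjusted variance is (1+ρ)/2, which is below 1 for any ρ below 1.

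**Conclusion.** The point holds. The plan fixes no primary outcome, time point or success rule, and does not establish control of error across outcomes. The powered test is not a direct test of improvement if baseline is a repeated measure, as the measurement schedule implies.

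The percentages rest on assumed correlations and on named rules. A reader might take 0.5-4% and 9-14% as the limits of the error rate, or 9-14% as the trial's actual rate. Neither is supported: other unwritten rules give roughly 0% to 18%, and the plan commits to none of them.

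On power, the conclusion that does not depend on the meaning of f = .398 is comparative. For outcomes with three occasions, the baseline-adjusted discharge comparison has more power than the between-factor test in both readings (63/71/86% against 51/43/37%, or 93/96/99% against 85/76/68%).

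**What to change.** Before any data are seen by group:

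1. Make the baseline-adjusted group difference at discharge, two-sided 0.05, the confirmatory comparison. Discharge is the only post-treatment point with all three outcomes.
2. Fix one rule, for example pain, then QuickDASH, then SODA, stopping at the first non-significant result. The sponsor may choose another order, or require both pain and QuickDASH.
3. State that a claim covering both pain and function needs both pain and QuickDASH to be significant.
4. Label group main effects, group-by-time tests, 3-month results and any MANOVA as supportive, and say what the Bonferroni comparison covers.
5. Reconcile the pain scale between sections and name the SODA score.
6. Restate the power for the chosen comparison, saying which meaning of f = .398 is used.

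**Cost.** A few sentences; no added patients are asked for, and the first outcome keeps the full 0.05. The downside is that a later outcome cannot be confirmed if an earlier one fails. If d is 0.796 at discharge, 16 per arm gives the joint pain and QuickDASH claim only about 37-53/49-63/72-81% power at ρ = 0.3/0.5/0.7 (between-outcome correlation 0 to 0.9). For information, 80% would need roughly 28-32/23-26/16-19 per arm for the joint claim and about 25/21/15 for pain alone, before dropout.

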- **Number of subjects:** N=32 (16 in each group)
- **Gender of subjects:** Both male and female participants will be included in the study. Demographic data will be included in the analysis of results.
- **Age of subjects:** 18-65yrs old
- **Racial and ethnic origin:** There will be no racial or ethnic restrictions to this study. Data on racial/ethnic origin will not be gathered by the researchers. It is assumed based on current client population that the sample will be diverse.
- **Inclusion criteria:**
 - i. Positive Finkelstein's test: The client will report pain over the first compartment of the extensor retinaculum when the thumb is tucked in the hand and deviated ulnarily.
 - ii. Persistent symptoms for >3 wks which have not resolved after an additional 3 weeks of splinting
 - iii. A diagnosis by a physician of "de Quervain's", "fist compartment tenosynovitis", or "radial styloid tenosynovitis"
 - iv. Patients must agree and comply to a predetermined splinting regimen
- **Exclusion criteria:**
 - i. History of cortical steroid injection to affected wrist and/or thumb
 - ii. Comorbidity such as osteoarthritis, rheumatoid arthritis, auto-immune disease or inflammatory conditions.
 - iii. Clotting deficits
 - iv. Positive Cozen's sign which would indicate intersection syndrome³⁸
 - v. Post-partum mothers <6 months and pregnant women¹⁰⁻¹¹
 - vi. Cleared c-spine via Spurling's Test³⁴⁻³⁵ performed by combining cervical extension, side-bending, and axial compression to the cervical spine.
- **Vulnerable subjects:**
No vulnerable subjects will be included in this study

III. Methods and Procedures:

- **Methods and procedures:**
 - i. Randomized selection of 2 groups both seen for one evaluation and 12 therapy sessions scheduled 2x/week for 6 weeks (total of 12 sessions) for either traditional therapy including splinting and exercises or traditional therapy with Astym protocol. At least 2 days in between therapy sessions to allow sufficient healing.
 - ii. Randomization using computer-generated random numbers. The 3 Outcome measurements will be taken during evaluation and re-evaluation will be collected by two designated hand therapists other than the treating therapist. The data collectors will be blinded.

- iii. Data collection are taken at baseline, and after 12 sessions of therapy at discharge. . Quick DASH and VAS scale scores and questionnaire regarding patient compliance will be completed by phone interview at 3 month follow up.

Research design:

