Patients with the diagnosis of de Quervain's from referring physician will be provided with a pre-fabricated Ossur thumb spica splint for use as indicated in splinting program^{13,15-17}, instructed on a home exercise program as part of standard of care along with being educated about the research study. If interested, they will be consented, and scheduled for a follow-up visit 3 weeks later. If not interested, they will be scheduled for a 3 week follow-up session and treated if needed. Upon their return, the patients will be screened by the researcher OT for inclusion and exclusion criteria. If subject meets the criteria, they will be randomized into either (1) control or (2) Astym group and then evaluated by a blinded Certified Hand Therapist or hand therapist. Fine motor coordination will be tested by using the Sequential Occupational Dexterity Assessment (SODA)³⁹. Pain and functional loss will be measured via the Visual Analog Scale (VAS)⁴⁰ and Quick Dash⁴¹⁻⁴⁵. They are then seen for formal therapy 2/x for 6 weeks for a total of 12 therapy session. If the subject does not meet criteria or decide not to participate in

the study, they are deemed a screen failure, dismissed from study, and will continue with treatment if needed.

The subjects will be seen twice a week for 6 weeks for 30 minute sessions by a separate treating therapist from the evaluating therapist. The patient will start at phase I; however, will not progress to the next phase of treatment if symptoms and pain are provoked.. When he/she tolerates exercises without pain or exacerbation of symptoms, the patient is progressed to Phase II and then phase III .Prior to discharge, if the subject has not achieved phase III, the therapist will incorporate Phase III exercises, for strengthening and functional movements of the hand, forearm, elbow and shoulder to be completed at home. . All subjects, either in control or Astym group, will receive only 12 sessions of therapy regardless if they progress through the all 3 phases. Astym group will receive traditional therapy with Astym every session, while the control group will only receive traditional therapy. See protocol below.

Control group: Traditional therapy for de Quervain's Tenosynovitis^{17-19, 21-22, 30-33:}

Phase I: Reduction of splint use andstrengthening initiated once patient can perform pain free AROM (monitor symptoms to not exacerbate condition)

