- Curriculum Vita for each investigator in study related documents

VI. Subject Identification, Recruitmet and Consent/Accsent

Method of subject identification and recruitment

Clients referred to NYU Langone Center for Musculoskeletal Care with a diagnosis of de Quervain's, radial styloid tenosynovitis, or first compartment tendonitis will be screened by investigators. After initial evaluation by a non-treating, blinded therapist, the patient will be provided with consent form and information on study (Appendix VIII). The client will be given the opportunity to ask questions to clinician and/or any member of the research team at this time or throughout the course of their treatment.

Process of Consent

Clients will be provided with consent form and information on study following the

clinician's inspection and determination of appropriateness to participate.

Subject Capacity

All clients who are unable to provide informed consent will not be included in this research study.

Subjects Representation Comprehension

Clients who are unable to understand the informed consent sheet and/or the educational hand outs and home exercise plan will not be considered for this study. The participants will be able to ask questions and request further information upon consent.

Debriefing Procedures

Clinicians will provide participants with measurements and results at any time throughout this study upon participant request. As is standard procedure at NYU Langone Medical Center clients have the right to access their medical records at any time which will include all measurements.

Consent forms-See study related documents

Documentation of Consent

All signed consent forms will be stored in a locked draw of a locked office. Consent forms along with all patient documentation will also be scanned into Epic and be available within the clients chart as is standard protocol here at NYU Center for Musculoskeletal Care. Participants will also be provided with a copy of signed consent form.

Costs to Subjects

There will be no additional cost to subjects for participation in this study. The use of the ASTYM therapy technique is combined with other therapeutic techniques and modalities and is billed accordingly at NYU Center for Musculoskeletal Care.

References Cited:

1. J.S. Moore, **De Quervain's tenosynovitis. Stenosing tenosynovitis of the first dorsal compartment.** J Occup Environ Med, 39 (1997), pp. 990–1002

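### The protocol names four possible Astym reactions but describes no systematic recording or by-arm summary of them; a brief per-session tally would be a cheap, optional improvement

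*Combined protocol and SAP*

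**What the plan says.** Section IV, under Risk, opens its list with "Potential side effects of Astym treatment include" and names four: bruising of the treated area, "Increased pain or soreness for 24-48 hrs after treatment", increased inflammation of the limb, and a vagal response such as faintness or nausea. Under Protection against risks, the measures are patient education, icing, eating beforehand, and that patients are "encouraged to tell their therapist to stop treatment if they do not wish to continue if they are experiencing any of these symptoms".

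The planned data are narrower. Section I, Study design, states: "Three outcomes measures will be used for the study". These are a pain rating, Quick DASH and SODA. Section III, Methods and procedures, item iii, gives the timing: "Data collection are taken at baseline, and after 12 sessions of therapy at discharge". It adds a 3-month phone interview for Quick DASH, VAS and compliance. Section III, Data Analysis and Monitoring, covers a mixed ANOVA, a possible MANOVA and power. It mentions descriptive statistics without linking them to reactions.

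There are informal routes. Under Research design in section III, a patient "will not progress to the next phase of treatment if symptoms and pain are provoked". The first treatment phase in both arms asks the therapist to watch symptoms. Section VI, Documentation of Consent, says: "Consent forms along with all patient documentation will also be scanned into Epic and be available within the clients chart". On assessment, section III, item ii, says: "The data collectors will be blinded".

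**The concern.** The trial asks whether adding Astym to standard therapy leaves patients better off. The background in section I describes a treatment that works by deliberate small tissue injury and a local inflammatory response, so local reactions are plausible consequences of the intended mechanism. The protocol anticipates them by name, yet the data it describes contain no item for them.

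If the plan is followed as written, benefit is reported by arm, but there is no systematic count by arm of bruising, soreness, inflammation or faintness. There is also no control-arm count of soreness from stretching and strengthening alone, which is what the Astym figure would need to be read against. Reactions that nobody asked about cannot be reconstructed at the analysis stage.

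**Working it through.** **Inputs.** 16 patients per arm, 32 in all (section II, Number of subjects). 12 sessions each, at least 2 days apart (section III, item i). Astym at every session in the Astym arm, 30-minute sessions, and a treating therapist separate from the evaluator (section III, Research design). The documents give no reaction rate, and none is assumed here.

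**Step 1: exposure.** Astym sessions: 16 x 12 = 192 at most. Sessions in both arms: 32 x 12 = 384.

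**Step 2: each reaction set against what the plan collects.**

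| Reaction | Pain, Quick DASH, SODA at baseline and discharge | 3-month call | Informal routes |
|---|---|---|---|
| Bruising | No item | No item described | Session notes, if written |
| Soreness for 24-48 h | Could worsen a score if present at discharge; not identifiable as a reaction | Long past | Symptom watching; patient may ask to stop; notes |
| Inflammation | Could worsen a score if it lasts to discharge; not identifiable as a reaction | No item described | As above |
| Vagal response | No item | No item described | Patient may ask to stop; notes |

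Soreness lasting 24-48 h after sessions 1 to 11 could be over by the next visit, given the spacing of at least 2 days, and so before discharge. It would be known only if the patient were asked or volunteered it.

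**Step 3: do the informal routes amount to a record?** Symptom watching serves exercise progression. Asking to stop captures reactions troublesome enough to interrupt a session, but not bruising or soreness that develops later at home. Scanning to the chart preserves what was written; it does not require anyone to ask. The protocol does not describe the content of session notes, so they could be incomplete or unstandardised, but this cannot be stated as fact.

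**Step 4: what a tally would cover.** Vagal events during treatment: all 192 Astym sessions. Delayed reactions, asked about at the following visit: 16 x 11 = 176 sessions, because nothing follows session 12.

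**Step 5: precision.** With 0 events in 16 patients, the one-sided 95% upper limit is 1 - 0.05^(1/16) = 0.171, or 17%. For an illustrative 4 of 16 (25%), the exact two-sided 95% interval is 7% to 52%. The counts can describe but cannot support a comparison.

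**Step 6: cost.** 384 entries at an assumed 1 minute: 384/60 = 6.4 h. At 2 minutes: 768/60 = 12.8 h. Per 30-minute session this is 1/30 = 3% to 2/30 = 7% of the time.

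**The case against.** The strongest reply is that nothing the trial sets out to estimate depends on this. The hypothesis in section I concerns pain and function. The device is described as non-significant risk and has been used at the centre for 4 years. Patients with clotting deficits are excluded, and section IV calls some of the side effects temporary. All of this stands, and it is why the point is optional.

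Second, part of the file is not available. The consent form, Appendix VIII, the schematic and the withdrawal criteria may contain reporting or stopping rules. This stands too. The point covers only the text available, and if such rules exist a cross-reference would be enough.

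Third, recording could do harm. No sham is described, so patients would know their treatment. Repeated, itemised questions about soreness could influence self-rated pain, possibly differently by arm, in a 32-patient trial with pain among its three outcomes. This carries weight and argues for a light tally with an open question, not a detailed checklist.

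A reader might infer that no reaction would be noted at any of the 192 sessions. The documents do not support that: therapists watch symptoms, patients are told to speak up, and documentation goes into the chart. A reader might also infer that patients are unprotected or that the efficacy comparison is compromised. Section IV gives protective measures, and the planned ANOVA uses none of the missing data.

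**Conclusion.** The gap is real but modest. The available text names four reactions and describes neither systematic recording in either arm nor a summary by arm, over up to 192 Astym sessions and 384 sessions in all. The consequence is that the trial could report benefit by arm without a comparable account of harms. It gives no ground for inferring danger.

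The conclusion assumes that the unavailable parts contain no such rules and that session notes follow no common form for these reactions. If either assumption is wrong, the point shrinks to a missing cross-reference or a missing table. The improvement is optional, and any counts obtained would be descriptive only.

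**What to change.** In section III, under Methods and procedures and Research design, have the treating therapist complete one brief yes/no tally per session in both arms:

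- bruising or swelling seen;
- soreness or other reaction reported since the last visit, from one open question without itemised soreness prompts;
- vagal event during the session;
- treatment withheld, and why.

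At session 1 the first two items serve as baseline. An explicit no then differs from a question not asked.

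Keep the tally as a research record in the locked study file already provided for under Data Storage and Confidentiality. State that it is not part of the documentation scanned into the chart. Keep it from the blinded evaluators until the patient's 3-month call is done. In Data Analysis and Monitoring, add one table of patients with each reaction by arm, with no test.

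The cost is a short amendment, 384 entries (about 6 to 13 therapist hours at the assumed 1 to 2 minutes each), data entry and one table. The remaining downsides are that the recorder is unblinded, asking may slightly raise minor reports or influence self-rated pain, and delayed reactions to session 12 are missed. The report should say so.
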